Adults with refractory IIM will be enrolled. IIM is defined as Dermatomyositis (DM) or Polymyositis (PM), meeting the Bohan & Peter (1975) diagnostic criteria for definite or probable DM or PM. Refractory IIM is defined as chronic active IIM with a history of inadequate response or intolerance to three months of glucocorticoids and/or at least a history of inadequate response or intolerance to three months of one other immunosuppressive agent (IS) (azathioprine, methotrexate, mycophenolate mofetil, leflunomide, tacrolimus, cyclosporine, cyclophosphamide, Rituximab or intravenous gamma globulin [IVIG]).

Study Objectives:

[figure not shown]
- a. To compare the clinical response rates in refractory IIM patients on stable background treatment receiving monthly intravenous (IV) belimumab to patients receiving placebo.
- b. To assess the safety of monthly IV belimumab in patients with IIM.
- c. To evaluate the steroid-sparing effect of monthly IV belimumab added to background treatment of IIM.
- d. To evaluate the biologic effects of belimumab treatment on various B cell populations and inflammatory cytokine levels.

Study Design:

This is a multicenter randomized double-blind placebo controlled trial to evaluate the efficacy and safety of Belimumab as a maintenance therapy in adults with refractory idiopathic inflammatory myositis (IIM).

The Northwell Health Department of Rheumatology will be the coordinating site for this multi-center clinical trial. We plan to enroll 30 patients into the trial. Enrollment is competitive. Study enrollment will be carried out for two years and each patient will be followed for a total of 84 weeks.

Figure 1. Study Flowchart-overview (please check Study Schedule, Appendix A for details).

At point A, a loading dose of Belimumab will be given at week 2.

At point B, a loading dose of Placebo (saline) will be given at week 2.

a. Study Procedures and Schedule:

A simplified flowchart of the study procedure is given in Figure 1.

After consent, a patient will be randomized to either Belimumab+ standard of care (B) or Placebo+ standard of care (P). Randomization will be according to the two important stratification variables, namely, disease type (Polymyositis vs. Dermatomyositis) and disease severity (severe vs less severe) and will occur at week 0 (first infusion). There will be two major study phases: the randomized phase of the study and the open-label phase of the study, described below.

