Belimumab and placebo will be supplied as open-label vials and 3rd party unblinding will be employed. The study agent will be reconstituted and diluted by the unblinded site pharmacist or designee, independent of the study (person responsible for receiving and dispensing study agent). Separate monitors will be responsible for the clinical (blinded monitor) and study agent (unblinded monitor) aspects of the study.

If a medical emergency occurs and a decision regarding the subject's condition requires knowledge of the treatment assignment, the study blind may be broken for the specific subject. Whenever possible, the investigator should consult with the principal investigator of the study and data safety monitoring board prior to unblinding any subject. Any broken blind will be clearly justified and explained. The lead site and sponsor must be notified of any broken blind regardless of whether it was done for emergency or non-emergency reasons.

e. Concurrent Medications:

Corticosteroids: Patients that are on glucocorticoids at the time of screening will be required to be on a stable background dose for at least 2 weeks prior to screening (prednisone (or equivalent) dose \leq 15 mg daily).

The prednisone dose will remain stable until week 24 of the study, at which time a taper will be allowed at the discretion of the site investigator and principal investigator.

An increase in the dose of oral prednisone will be permitted, if clinically necessary, during the first 8 weeks after randomization without accounting it as a disease flare. In this case, the dose of prednisone must be tapered (to less than or equal to 25% of the baseline dose) by week 12. However, if the dose of prednisone cannot be tapered by week 12, the event will be considered as disease flare at that time.

Any increase of the prednisone dose after week 8 for IIM disease activity or the use of pulse steroids at any time during the study will be considered a disease flare. An increase of the prednisone dose at any time during the study for an event other than worsening of IIM disease activity will require the patient to return to the baseline dose of prednisone within 10 days, without accounting the event as a disease flare. Patients that are considered treatment failures will be allowed to remain in the study, in respective groups, at the discretion of the treating physician and PI.

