Immunosuppressive agents (IS): Enrolled patients could have had a history of treatment with any of the following IS agents: azathioprine, methotrexate, mycophenolate mofetil, leflunomide,

tacrolimus, cyclosporine, cyclophosphamide, Rituximab, or intravenous gamma globulin [IVIG]. Patients are not required to be on an IS agent at the time of enrollment.

During the enrollment and study period, the only allowed IS agents are: azathioprine, methotrexate, mycophenolate mofetil, tacrolimus, cyclosporine or intravenous gamma globulin [IVIG].

Patients that are on background immunosuppressive (IS) therapy at the time of screening will be required to be on a stable IS agent for \geq 2 months prior to screening (\geq 3 months for IVIG), and on a stable dose of IS agent for \geq 2 weeks prior to screening (except IVIG; no dose change allowed). Dose reduction due to poor tolerance of IS agent will be allowed on a case by case basis.

Therapeutic Agent	Treatment Duration prior to Screening \geq	Dose Increase prior to Screening \geq
Azathioprine	2 months	2 weeks
Methotrexate	2 months	2 weeks
Mycophenolate mofetil	2 months	2 weeks
Tacrolimus	2 months	2 weeks
Cyclosporine	2 months	2 weeks
IVIG	3 months	none

If a dose increase in IS agent or initiation of a new IS agent is clinically necessary during the randomization phase, this will be considered as a disease flare. The patient will be allowed to continue in their respective assigned group at the discretion of the treating physician and PI.

f. Medications and Therapies Prohibited for Concomitant Use:

a. Anti-B-cell therapy:

- i. Wash out of 5 therapeutic half-lives after prior B-cell therapy, or until pharmacodynamic effect would be minimal (e.g., 1 year following Rituximab)
 - IgG levels should be measured monthly in this situation
 - Benlysta should be discontinued in subjects with IgG levels <250 mg/dL associated with a severe or serious infection
- ii. If Rituximab use was medically indicated after the patient's enrolment to the clinical trial, the patient will no longer receive the investigational drug, but enhanced safety monitoring will be required.

b. Intravenous Cyclophosphamide

- i. 180 Days Prior to Belimumab
 - IgG levels should be measured monthly in this situation
 - Benlysta should be discontinued in subjects with IgG levels <250 mg/dL associated with a severe or serious infection

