3. an increased dose of corticosteroid before study week 8 and did not return to $<25\%$ above the baseline dose by week 12.

Endpoints:

1. **Primary Endpoint:**
 - a. Response rate at 40 weeks defined as percentage of patients meeting definition of improvement (DOI) in IIM patients treated with belimumab and standard therapy compared to the percentage of patients meeting DOI treated with placebo and standard therapy.
2. **Secondary Endpoints:**
 - a) Incidence of flares: flare rates during 40 weeks randomization period in patients with IIM treated with belimumab and patients treated with placebo and at week 64 in each group.
 - b) Time to achieve initial improvement defined as the time to reaching DOI.
 - c) Duration of improvement; quantified as the time from achieving improvement to the time of worsening or a disease flare. (Time from 1st DOI to 1st DOW or disease flare event). This will be based on the subset of subjects who achieve improvement.
 - d) Percent change in muscle enzyme levels (CPK and myoglobin) from baseline to week 40 and 64 in each respective group
 1. $<20\%$ reduction: no response
 2. 20-70% reduction: partial response
 3. $>70\%$ reduction: complete response
 - e) Percent change in manual muscle assessment (MMT-8) from baseline to week 40 and week 64 in each respective group.

- 1. <20% reduction: no response
- 2. 20-70% reduction: partial response
- 3. >70% reduction: complete response
- f) Percent change in prednisone dose from baseline to week 40 and week 64 in each respective group
- g) Proportion of subjects, among those on steroids at baseline, able to reduce the prednisone dose to ≤ 5 mg daily at week 40 and week 64 in each respective group.
- h) Flare rate in placebo group during the 40 week randomized treatment phase as compared to that group in the 20 week open label phase.
- i) Serious adverse event and adverse event rates
- j) Changes in B cell populations from baseline to week 40 and week 64
- k) Changes in autoantibody titers from baseline to week 40 and week 64
- l) Changes in immunoglobulin concentrations from baseline to week 40 and week 64

Inclusion Criteria:

Subjects enrolled in the study must meet the following inclusion criteria:

- 1) Adults ≥ 18 years of age
- 2) Have a diagnosis of:
 - a. definite or probable dermatomyositis (DM) by modified Bohan & Peter criteria or

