The Biostatistics Randomization Management System (BRMS) is a secure, HIPAA-compliant, web-based application that allows investigators to randomize subjects into randomized clinical trials (RCTs) using their personal computer. The BRMS allows for multi-center, stratified, and single/double blinded RCTs, using permuted blocks. Randomization notifications are automatically sent to the PI and other authorized personnel. Using BRMS is a good way to maintain compliance in RCTs.

Statistical Considerations

SPECIFIC STATISTICAL AIMS

The primary objective of the study is to compare subjects in the Belimumab group and subjects in the placebo group with respect to response (improvement) at week 40.

The specific aims of the study are to compare the two treatment arms (Belimumab vs. Placebo [P vs. B]), during the 40-week randomized phase of the study, with respect to the following:

1. Response at week 40.
2. Flare rates during the 40-week treatment period.
3. Time-to-achieve (initial) improvement during the 40-week randomized phase of the study
4. Duration of improvement during the 40-week randomized phase of the study, among those who achieved improvement (this is essentially a time-to-flare/relapse analysis from the time that you achieved improvement)
5. Change in muscle enzyme levels (CPK, myoglobin) from baseline to week 40
6. Change in MMT-8 from baseline to week 40
7. Change in prednisone dose from baseline to week 40

8. Proportion of subjects able to reduce prednisone dose to ≤ 5 mg at week 40
9. Change in B cell populations, immunoglobulin levels and BLys levels from baseline to week 40.
10. Change in autoantibody titers from baseline to week 40.
11. Rates of SAEs and AEs experienced

STATISTICAL METHODS

All subjects will be analyzed according to the intention-to-treat [ITT] principle. A subject will be considered evaluable and will be included in the intention-to-treat analysis if he/she received at least the first five of the planned infusions during the randomized phase of the study. Subjects who do not get the first five infusions will be considered ‘drop-outs’. It should be noted that the study protocol calls for patients remaining on their treatment assignment. However, adjustments in dosages of medications used in their ‘standard care’ are permitted during the first 8 weeks. Analyses that take into account the actual treatment received (e.g. accounting for compliance, etc.) will be carried out as a secondary analysis (per protocol [PP] analysis).

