treatment and time (baseline vs. week 40; or all available data at each study visit) or other factors of interest will be examined (e.g. Treatment X Disease Type; Treatment X Disease Severity). The treatment-by-time interaction term, will demonstrate whether the trajectories (or patterns of change) in the outcomes of interest are different between treatment groups. Data transformations may be used, in order to meet the necessary assumptions for the mixed models analyses. If transformations do not achieve the assumptions needed, a rank transformation or an appropriate non-parametric method will be considered.

If the analysis using a mixed model approach is not feasible due to the pattern of the data, then, a simplified analysis comparing the two treatment arms with respect to percent change (reductions) in muscle enzymes, MMT-8 and prednisone dose will be carried out using either a t-test or the Mann-Whitney test, as appropriate. A chi-square test or Fisher's exact test, as appropriate, may also be used if the continuous measures are grouped according to pre-specified categories (e.g. reduction in CPK will be categorized as No Response, Partial Response or Complete Response according to whether the percent reduction was <20% vs. 20%-70% vs. >70%, respectively).

6. For specific aim 8, the proportion of subjects who were able to reduce their daily prednisone dose to ≤ 5 mg at week 40, will be compared using either a chi-square test or Fisher's exact test, as appropriate.
7. For specific aim 11, either a chi-square test or Fisher's exact test, as appropriate, will be conducted to compare the proportion of subjects who experienced any SAEs or AEs during the randomized phase of the study. For this analysis, each subject will be categorized at the end of 40 weeks as having had any SAEs/AEs or not having any SAEs/AEs.

Multivariable analyses (logistic, cox) will be conducted for the above outcomes, if feasible. However, this may be limited by the sample size.

SAFETY DATA

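### The steroid-sparing endpoints score prednisone dose with no rule for rescue, so a patient at the 5 mg limit at week 40 after rescue counts as spared, and the arm difference can be distorted in either direction

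*Combined protocol and SAP*

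**What the plan says.** Study Objectives, item c, is "To evaluate the steroid-sparing effect of monthly IV belimumab added to background treatment of IIM". Two secondary endpoints serve it.

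- **Endpoint f / aim 7:** "Change in prednisone dose from baseline to week 40" (endpoint f uses percent change and adds week 64). Statistical Methods item 5 analyses it with a mixed model. The main time factor is baseline v week 40. The interaction to be examined, if feasible, is between "treatment and time (baseline vs. week 40; or all available data at each study visit".
- **Endpoint g / aim 8:** endpoint g is the "Proportion of subjects, among those on steroids at baseline, able to reduce the prednisone dose to" 5 mg daily or less at weeks 40 and 64. Aim 8, the "Proportion of subjects able to reduce prednisone dose to" 5 mg or less at week 40, drops the restriction to baseline steroid users. Statistical Methods item 6 compares "the proportion of subjects who were able to reduce their daily prednisone dose to" that limit by chi-square or Fisher's exact test.

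Study Design, section e (Concurrent Medications), permits the events at issue. Starting or increasing an immunosuppressant in the randomized phase is a flare, and IVIG is among the allowed agents. After that, "The patient will be allowed to continue in their respective assigned group at the discretion of the treating physician and PI". For steroids, "the use of pulse steroids at any time during the study will be considered a disease flare", and treatment failures may also remain in their group. Oral prednisone is held stable to week 24, after which a taper is discretionary.

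**The concern.** Flares enter aim 2 (any flare) and aim 4 (duration of improvement). Nothing carries them into aims 7 or 8: there is no failure rule, no composite and no censoring at rescue. Consider a patient who flares at week 14, starts a new agent, and is tapered to 5 mg after week 24. That patient is a flare in aim 2 and a steroid-sparing success in aim 8.

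A second agent is itself a means of lowering prednisone. The objective concerns belimumab added to background treatment, so the endpoint may credit the rescue drug to whichever arm used it. If belimumab works, more rescue on placebo is plausible, and the comparison then moves towards zero. If rescue runs the other way, the endpoint flatters belimumab.

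Aim 7 has a related gap. Rescue without prednisone is invisible to it, and a steroid pulse given between assessments need not appear in it, even if all visits are modelled.

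**Working it through.** **The plan's own figure.** The plan states no rate or power for the steroid-sparing aims. Its only sample-size figure is for the primary endpoint: 5% v 50%, two-sided alpha 0.05, 80% power. With the pooled chi-square formula, n = [1.96 x sqrt(2 x 0.275 x 0.725) + 0.8416 x sqrt(0.05 x 0.95 + 0.50 x 0.50)]^2 / 0.45^2 = 2.879 / 0.2025 = 14.2, so 15 per arm. This reproduces the plan, with 82.3% power at n = 15. It says nothing about aims 7 and 8.

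**Formula for aim 8.** For each arm let r = share rescued, s = success among the unrescued, and q = share of the rescued at 5 mg or less at week 40 (taken as equal in both arms).

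- Dose-only rate = (1 - r)s + rq
- Rescue-as-failure rate = (1 - r)s
- Dose-only difference = rescue-as-failure difference - q x (r placebo - r belimumab)

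**Base illustration.** All rates are assumed, because the documents give none: r = 50% placebo and 20% belimumab; s = 15% and 50%; q = 50%.

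- Dose-only: belimumab 0.80 x 0.50 + 0.20 x 0.50 = 50.0%; placebo 0.50 x 0.15 + 0.50 x 0.50 = 32.5%; difference 17.5 points.
- Rescue as failure: belimumab 0.80 x 0.50 = 40.0%; placebo 0.50 x 0.15 = 7.5%; difference 32.5 points.
- Shift: 0.50 x (50 - 20) = 15 points, which is the whole gap between the two.

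Power by exact enumeration, two-sided 5%, chi-square without continuity correction:

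| Per arm | Test | Dose-only | Rescue as failure |
|---|---|---|---|
| 15 | Chi-square | 16% | 60% |
| 15 | Fisher | 7.5% | 41% |
| 10 (assumed) | Chi-square | 11% | 35% |
| 10 (assumed) | Fisher | 4% | 19% |

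Fifteen per arm is an upper bound, because endpoint g covers only baseline steroid users. Under rescue as failure the expected number of successes is 15 x (0.40 + 0.075)/2 = 3.6 per arm, so Fisher is the likelier test.

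**Sensitivity, same s, 15 per arm, chi-square.**

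| Rescue placebo / belimumab | q | Dose-only: points (power) | Rescue as failure: points (power) |
|---|---|---|---|
| 30/10 to 60/30% | 30-70% | 8 to 28.5 (7-39%) | 29 to 34.5 (54-61%) |
| 30/30% | 30-70% | 24.5 (26-32%) | 24.5 (38%) |
| 20/30% | 50% | 28 (37%) | 23 (33%) |

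In the last row, dose-only is 50.0% - 22.0% and rescue as failure is 35.0% - 12.0%. Dilution therefore needs more rescue on placebo; reversed rescue inflates the difference.

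**Aim 7.** A patient on 10 mg/day for 40 weeks takes 10 x 280 = 2,800 mg. An assumed three-day pulse of 250 to 1,000 mg/day prednisone-equivalent adds 750 to 3,000 mg. If that patient is back on the baseline dose at week 40, the week 40 change is still zero.

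**The case against.** The strongest defence is that the week 40 dose regardless of rescue is a recognised treatment-policy reading. It fits the stated intention-to-treat principle, flares are reported beside it, and a per-protocol analysis is named as secondary. That is a fair reason to keep the dose-only comparison. It does not close the gap: the intention-to-treat paragraph says who is analysed, not how rescue is scored, and the per-protocol analysis has no rescue rule.

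The second objection is that a composite can create apparent sparing. Suppose unrescued success is 50% in both arms, rescue is 20% belimumab v 50% placebo, and q = 50%. The dose-only rates are then 50% v 50%, while the composite gives 0.80 x 0.50 = 40% v 0.50 x 0.50 = 25%. That 15-point effect consists only of rescue use, which aim 2 already tests. This stands, and it is why the composite should sit beside the dose-only version with rescue reported by arm.

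Stronger readings are tempting but unsupported:

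- A reader might infer that every rescued patient is scored as steroid-spared. Aim 8 still requires 5 mg or less at week 40, and rescue by higher oral prednisone still in force then is captured by the dose. A pulsed patient back on the baseline dose shows no change in aim 7, which is not a success.
- A reader might infer that both aims read only the week 40 dose. That is true of aim 8, but item 5 allows all visits for aim 7.
- A reader might infer that the difference is necessarily diluted. The documents give no rescue rates, and equal or reversed rescue gives no dilution or the opposite.

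**Conclusion.** The concern holds in a limited form. The plan classes these rescues as flares, keeps the patients in their arms, and then lets a rescued patient at the 5 mg limit count as steroid-spared without saying that this is intended. Aim 7 does not account for non-prednisone rescue and can miss pulses.

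The effect on aim 8 is q x (placebo rescue - belimumab rescue), with q equal in both arms. The 17.5 v 32.5 points and the matching powers are an illustration on assumed rates at the largest possible arm size. They are not a forecast, and the whole gain in points comes from the assumed excess of rescue on placebo. Without a stated rule, a difference in aim 8, or its absence, cannot be attributed to belimumab rather than to rescue. The aims are secondary and carry no stated power, so this should be corrected but does not touch the primary endpoint or its sample size.

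**What to change.** Before unblinding:

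1. **Aim 8, endpoint g and item 6.** Keep the dose-only comparison and label it treatment-policy. Beside it, pre-specify a rescue-as-failure analysis: success is prednisone at the plan's own limit at week 40 and no disease flare from randomisation through week 40; otherwise failure. In the formulas above, r then means the share with any flare. State one denominator, since endpoint g and aim 8 differ.
2. **One flare definition.** The sections disagree and must be reconciled first. Section e counts an immunosuppressant start or increase at any time in the randomized phase; the Disease Flare definition counts it only after week 8; Statistical Methods permits standard-care dose adjustments in the first 8 weeks. Section e counts pulse steroids at any time, which the Disease Flare definition does not state. The two also word the week 12 condition after an early prednisone increase differently: one relative to 25% of the baseline dose, the other to 25% above it.
3. **Report rescue by arm** (agent, timing, pulses) with both analyses, so that a difference made only of rescue use is visible.
4. **Aim 7 and endpoint f.** Add, as supportive, cumulative prednisone-equivalent exposure from week 0 to week 40, pulses included and adjusted for baseline dose, where dated doses are recorded.

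Cost: wording in the endpoint and statistical sections, with no change to any patient's treatment. Starts and increases are already needed for the flare endpoint, but cumulative exposure needs dated doses, and the Appendix A schedule shows no row for steroid dose or concomitant medication. There will be fewer successes in both arms, and the composite partly overlaps with the flare endpoint.

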Screening: Once the patient signs the consent form, a screening period of up to two weeks will initiate to determine the patient's eligibility for the study, prior to entering the randomization phase. Only eligible patients will enter the randomization phase.

Randomized Phase: Monthly infusions (of either B or P) will start at week 0 and continue every four weeks until week 36 (10 months) for the “randomized” phase of the study. In addition, there will be a “loading dose” at week 2 (per drug [IND] specifications). The loading dose will consist of either Belimumab or Placebo (saline) in the B or P treatment arms, respectively.

Open Label Phase: Monthly infusions (of B) will start at week 40 and continue every four weeks until week 64 (6 months) for the “open-label” phase of the study.

A comprehensive evaluation of the patient (Physical exam and history, vital signs, AEs, CBC and metabolic panel, GGT, myoglobin, pregnancy test, urinalysis, ESR, CRP, CPK, immunoglobulins, muscle and health evaluations, physician global assessment, patient self-assessments, serum level sampling) will be conducted at weeks 0, 8, 16, 24, 32, 39-40, 52, 64. A less comprehensive set of evaluations (vital signs, AEs, CBC and metabolic panel, GGT, pregnancy test) will be conducted at weeks 2, 4, 12, 20, 28, 36, 40, 44, 48, 56, 60. A detailed schedule of visits and procedures is outlined in appendix A.

A telephone follow-up conversation will also be conducted at weeks 72 and 84.

Optional Exploratory Studies

Blood based biomarker assessments and blood based RNA assessments will be performed on stored samples for consenting patients at Northwell Health only. See Appendix A (schedule of events).

b. Randomization:

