The Biostatistics Unit at the Feinstein Institute for Medical Research [BU-FIMR] will develop a web based randomization plan for the study. A randomization schema will be generated by the BU-FIMR for each participating site using the method of permuted blocks. Subjects will be randomly assigned in a 1:1 ratio to either Belimumab or Placebo, according to two stratification variables, namely, disease type (Polymyositis or Dermatomyositis) and disease severity (severe or less severe). The Biostatistics Randomization Management System (BRMS) is a secure, HIPAA-compliant, web-based application that allows investigators to randomize subjects into randomized clinical trials (RCTs) using their personal computer. The BRMS allows for multi-center, stratified, and single/double blinded RCTs, using permuted blocks. Randomization notifications are automatically sent to the PI and other authorized personnel. Using BRMS is a good way to maintain compliance in RCTs.

c. Stratification:

Randomization will be according to the two important stratification variables: disease type (Polymyositis vs. Dermatomyositis) and disease severity (severe vs less severe) and will occur at week 0 (first infusion). The number of immunosuppressive agents used by the patient over the last year (corticosteroids are not included) will be used as a surrogate of disease activity: one or less IS agent over last year versus more than 1 IS agent over last year.

d. Blinding:

This is a double-blind study; both the investigator and the patient will be blinded to the treatment assignment in the randomized phase of the trial. At the end of the 40 week randomized treatment phase all subjects will start the 20 week open label phase and therefore the drug will be dispensed in the unblinded fashion.

For each study site, there will be a designated unblinded research coordinator (URC) and a blinded research coordinator (BRC). The URC will be responsible for obtaining randomization assignments from the BU-FIMR and will oversee the preparation of infusions prior to drug administration. The BRC will be responsible for coordinating patient visits and administration or the infusion (infusion will be masked and not identifiable through any physical characteristics such as color or consistency, as the drug is of a powder form mixed in saline solution).

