
1. For specific aim 1, the two treatment arms [B vs. P] will be compared with respect to the proportion of subjects who respond to treatment at 40 weeks (improvement according to definition), using either a chi-square test or Fisher’s exact test, as appropriate.
2. For specific aim 2, either a chi-square test or Fisher’s exact test, as appropriate, will be conducted to compare the proportion of subjects who had any flares during the 40-week randomized phase. For this analysis, each subject will be categorized at the end of 40 weeks as having had one or more flares or not having had any flares. In addition, we can also examine the total number of days that a subject had a specific flare during the course of the 40-week treatment, and compare the two treatment arms using the ‘Incidence density ratio’ method.
3. For specific aim 3, standard methods for survival analysis will be carried out. The Kaplan-Meier (KM) product limit method will be used to estimate overall “time-to-achieve (initial) response/improvement”. Ninety-five percent confidence intervals will be calculated using Greenwood’s formula for computing the standard error. Subjects who have not achieved improvement as of week 40 will be considered ‘censored’ for the event (event=improvement/response).
4. For specific aim 4, similar methods as indicated for specific aim 3 will be conducted. The analysis for this aim will be limited to the subset of subjects in each treatment arm who show improvement at anytime during the randomized phase of the trial. A subject who has not flared/worsened/relapsed as of week 40 will be considered ‘censored’ for the event (event=flare/relapse).
5. For specific aims 5, 6, 7, 9 and 10, each of the outcome variables of interest (uncensored continuous or categorical) will be analyzed separately, using a mixed model approach to repeated measures analysis of variance (MMRMANOVA) with the main effects of treatment arm (B vs. P), Disease type (PM vs DM), Disease Severity (Severe vs. Less Severe) and time (baseline vs. 40 weeks). If feasible, statistical interactions between

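### The efficacy set labelled intention-to-treat admits only patients who received the first five infusions (to week 12), and no efficacy analysis of all randomised patients is planned

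*Combined protocol and SAP*

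**What the plan says.** In the combined protocol and SAP, Statistical Considerations, Statistical Methods opens with "All subjects will be analyzed according to the intention-to-treat [ITT] principle". The next sentence narrows this: a subject is evaluable and "included in the intention-to-treat analysis if he/she received at least the first five of the planned infusions during the randomized phase". Then: "Subjects who do not get the first five infusions will be considered" drop-outs. No outcome rule or analysis is given for them.

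The same paragraph names one other approach: "Analyses that take into account the actual treatment received (e.g. accounting for compliance, etc.) will be carried out as a secondary analysis", labelled per protocol. For specific aim 1 the arms "will be compared with respect to the proportion of subjects who respond to treatment at 40 weeks", and no other analysis set is named there.

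On timing, Study Design (part c, Stratification) puts randomisation at week 0, with the first infusion. The Randomized Phase paragraph says "Monthly infusions (of either B or P) will start at week 0 and continue every four weeks until week 36", with an added loading infusion at week 2.

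**The concern.** Intention-to-treat protects the comparison because membership is fixed at randomisation. Here it is fixed 12 weeks later, by treatment actually received, and assigned treatment can affect who gets that far:

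- After rituximab use, "the patient will no longer receive the investigational drug, but enhanced safety monitoring will be required"; Study Design part f has the same provision for cyclophosphamide.
- Appendix C stops study treatment after a liver stopping event.
- Study Drug Administration item 2 stops administration for a serious reaction, without saying whether later infusions follow. Item 3 reports that infusion reactions cluster on the first two infusion days, inside the five-infusion window.

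An early failure or an intolerant patient can therefore leave the primary denominator instead of counting in the assigned arm. Read literally, the rule also removes a patient who missed one early infusion but has a known week 40 response. The bias could run either way, depending on which arm loses patients and whether they would have met the definition of improvement (DOI) at week 40.

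**Working it through.** **1. When membership is settled.** The Randomized Phase paragraph and Study Drug Administration item 1 both give infusions at weeks 0, 2, 4, 8, 12 and so on. The fifth is at week 12; randomisation is at week 0.

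**2. The plan's own sample size.** Inputs from Sample Size Considerations: 5% v 50%, two-sided alpha 0.05, 80% power, 0% dropout. With p̄ = 0.275 and pooled variance under the null:

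n = [1.96·√(2p̄(1−p̄)) + 0.842·√(p₁(1−p₁)+p₂(1−p₂))]² / (p₂−p₁)² = 14.2, so 15 per arm, as stated.

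Power at 15 is Φ[(0.45·√15 − 1.96·√0.39875)/√0.2975] = Φ(0.926) = 82%. At zero dropout the evaluable and all-randomised sets coincide, so this calculation does not test the rule.

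**3. Sensitivity of one result to exclusions.** All counts are assumed. Chi-square is uncorrected.

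| Non-responders removed | Table (B v P) | Fisher p | Chi-square p |
|---|---|---|---|
| None | 6/15 v 1/15 | 0.080 | 0.031 |
| 1 B | 6/14 v 1/15 | 0.035 | 0.023 |
| 2 B, 1 P | 6/13 v 1/14 | 0.033 | 0.021 |
| 3 B, 3 P | 6/12 v 1/12 | 0.069 | 0.025 |
| 3 P | 6/15 v 1/12 | 0.091 | 0.062 |
| 1 B, 4 P | 6/14 v 1/11 | 0.090 | 0.062 |
| None | 10/15 v 3/15 | 0.025 | 0.010 |
| 3 P | 10/15 v 3/12 | 0.054 | 0.031 |

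**4. False difference in rates.** If both arms have the same all-randomised rate r and three of 15 non-responders leave one arm only, that arm's rate becomes r·15/12. At r = 20% it is 25% (5 points); at 40%, 50% (10 points); at 5%, 6.25% (1.25 points).

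**5. Type I error.** Full enumeration of two Binomial(15, p) arms, two-sided 0.05, with none v three belimumab non-responders removed. The switch rule (Fisher when any expected count is below 5) is assumed, because the plan leaves the choice open.

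| True rate, both arms | Fisher | Switch rule | Chi-square |
|---|---|---|---|
| 5% (plan's placebo rate) | 0.1 → 0.3% | 0.1 → 0.3% | 0.5 → 1.7% |
| 30% (assumed) | 1.7 → 4.5% | 2.9 → 5.6% | 5.5 → 9.3% |
| 40% (top of the plan's quoted placebo range, at 12 weeks) | 1.6 → 5.9% | 3.9 → 8.8% | 4.9 → 11.2% |

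False positives favouring belimumab (nominal 2.5%), by Fisher, go from 0.8 to 3.7% at 30% and from 0.8 to 5.4% at 40%. Random loss of three belimumab patients at 30% gives only 3.0, 3.3 and 5.7% for the three tests, so most of the increase comes from the loss being informative.

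**6. Power with all randomised patients analysed.** Worst case: a fraction d of each arm stops early and none respond, so rates become 5%·(1−d) and 50%·(1−d) with n = 15. Under the current rule, rates stay at 5% and 50% but n falls to 15(1−d).

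| d (assumed) | All randomised, normal approx. | Current rule, normal approx. | All randomised, Fisher | Current rule, Fisher |
|---|---|---|---|---|
| 10% | 76% | 78% | 66% | 73% |
| 20% | 68% | 72% | 57% | 65% |
| 30% | 60% | 66% | 46% | 55% |

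By the normal approximation, the all-randomised analysis has more power than the current rule once early stoppers respond at about 31, 28 or 24% of the others' rates. If they respond as often as the others, power stays at 82%.

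**The case against.** Several points against the concern are fair.

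- **Breadth.** The opening sentence does promise an analysis of all subjects, so the text contradicts itself. For adverse events no analysis set is named, so the absence of an all-randomised analysis is firm only for efficacy. Both limits stand, but the five-infusion rule is the operative one and nothing overrides it for the primary test.
- **Retention and blinding.** Study Design part e lets treatment failures stay in their group, and likewise patients needing more immunosuppression, at the discretion of the treating physician and principal investigator. The randomised phase is double-blind, and an infusion may be slowed rather than lost. This narrows the route to informative loss. It does not close it: retention is discretionary, and blinding does not stop toxicity or lack of effect from deciding who reaches infusion five.
- **Scale.** The type I scenario is severe: 20% of one arm, all non-responders. At the plan's 5% placebo rate, error stays below nominal. With one or two belimumab non-responders removed, Fisher stays under 5% (2.8 and 3.6% at a true 30%; 2.9 and 3.8% at 40%). The plan also cites 0% placebo response at 52 weeks. These figures show what is possible, not what is expected.
- **Mixed tests.** From 6/15 v 1/15, Fisher crosses 0.05 only towards significance and chi-square only away from it. That is true of that table; 10/15 v 3/15 shows Fisher alone crossing the other way.
- **Cost.** If the 30 evaluable patients in Sample Size Considerations implies replacement, the comparator is 82% and the worst-case cost is larger. No replacement rule is stated, and replacement would restore numbers but not the randomised comparison.

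**Conclusion.** The concern holds and must be fixed. The primary efficacy set is a post-randomisation evaluable set under an ITT label, and no efficacy analysis of all randomised patients accompanies it. This follows from the text and needs no assumption about dropout.

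The size of any bias is unknown because no early-stop rate is given, and its direction is not fixed. Under the assumed scenarios, one excluded patient can change the conclusion, and one-sided informative loss of three patients can take type I error above 5% at response rates of 30 to 40% (under Fisher, only at 40%). At the plan's 5% placebo rate it does not.

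**What to change.** - Define the primary set as all randomised patients, analysed in the arm assigned.
- Use observed week 40 DOI status regardless of infusions received. State that week 40 core set measures are collected from patients who have stopped infusions. Study Procedures & Assessments already schedules these measures at week 40, so this is explicit wording rather than a new visit.
- Pre-specify how a patient with no week 40 assessment is counted; non-responder is one reasonable choice.
- Keep the five-infusion set as a supportive analysis and call it evaluable.
- Restate the sample-size basis, which now counts 30 evaluable patients and assumes no dropout.

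The cost is mostly wording. Under the worst case at d = 10, 20 or 30%, the power loss against the current rule without replacement is about 2, 4 or 6 points by the normal approximation and about 7, 8 or 9 by exact Fisher. If patients would have been replaced, the loss is about 7, 14 or 22 points from 82% (normal approximation). Total N for 80% power would be 34, 40 or 48, against 32, 36 or 42 under the current rule. The better the week 40 follow-up of early stoppers, the further the real cost should fall below these figures if some of them respond.
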